#### ***Clinical Trial Phase:***

At the end of the sampling phase, eligibility for the clinical trial phase will be determined. Eligible subjects will have used an average of at least 2 sachets of Camel Snus daily during the sampling phase or at least 7 snus sachets used over most days during the sampling period. Subjects must be willing to attend clinic visits weekly for 4 weeks and biweekly visits for 6 weeks and a follow-up visit at 12 weeks post study product use and agree to be called at 4 and 24 weeks post-study. Subjects who wish to continue in the study will undergo 2 weeks of baseline where they will resume smoking and then will be randomized to one of five experimental conditions.

#### **Baseline smoking period:**

Subjects will be required to attend baseline clinic visits during Week -2 (visit 91) and -1 (visit 00) of the clinical trial phase, and they will record their cigarette or other tobacco intake on a daily basis using an interactive voice response system (IVR) (see Table 1).

First baseline visit: This baseline visit will assess tobacco use status to determine if smoking has returned to levels prior to sampling phase. Subjects will collect a first morning void urine sample and bring it in on the day of their clinic visit for study biomarkers.

24 hours prior to second baseline visit: Prior to the second baseline visit, subjects will collect all of their cigarette butts in a container provided for the entire day.

Second baseline visit: Subjects will collect a first morning void urine sample on the day of their clinic visit. The 24 hour cigarette butt collection and urine sample will be brought with them to their clinic visit. Blood samples will be drawn for study biomarkers. Buccal cells will be collected 20 minutes after the subject brushes their teeth using a cytobrush rubbed against the buccal mucosa as per previous studies (34). Oxygen saturation, CO, vitals and weight will be obtained. Subjective measures will include predictors for MRTPs use, factors that may influence the biomarker measures, and outcome measures (see Tables 1 and 2).

#### **Experimental period:**

After the baseline assessment, subjects will be randomized to one of five experimental conditions: 1) smoking usual brand cigarette controls, who after 8-weeks will be offered Camel Snus and instructed for partial or complete substitution of cigarettes (subject's choice); 2) complete substitution (i.e., no smoking) and *ad libitum* use of snus; 3) complete substitution (i.e., no smoking) and specific instructions for snus use based on the number of cigarettes smoked per day (if 10-20 cigarettes, use 8 pouches per day snus, and if >20 cigarettes then 12

pouches per day – these amounts were derived from a clinical trials conducted by us and by [name] and associates [personal communication]). 4) partial substitution with *ad libitum* use of both snus and cigarettes; and 5) partial substitution with controlled use of snus (paralleling the instructions for complete substitution condition) and *ad libitum* smoking. All subjects will be instructed to use the snus pouch for at least 5 minutes and optimally 30 minutes per occasion; Snus, but not cigarettes, will be provided to subjects at the clinic visits.

Procedures for clinic visits: Subjects will continue to complete daily diaries for tobacco and other nicotine product use. At every clinic visit, vital signs, weight, oxygen saturation and expired air CO will be obtained. At weeks 2, 4, and 8 of product use, blood, and first morning void urine collection samples will be collected. At week 6, a first morning void urine sample will be provided. Buccal cells will be collected at weeks 4 and 8. Samples from weeks 4 and 8 will be analyzed for biomarkers as described below. Samples taken at week 2 will be aliquoted and stored for future analyses governed by results from the 4 and 8 week analyses or for other future studies. Questionnaires that measure factors that may influence biomarker assessments will be administered at the time of biosample collection. All other subjective measures will be collected throughout the experimental phase. All cigarette butts, as appropriate for the study group, will be collected in a container 24 hours before the week 4 biomarker clinic visits. In addition, used and unused snus will be collected for 24 hours prior to week 4 to assess for amount of constituents that have been extracted. During this collection, time in and time out of snus products via a paper diary will be recorded to assess oral tobacco topography. At the end of experimental phase, all subjects will be strongly encouraged to quit using all tobacco products and set a quit date. A treatment manual (Clearing the Air) and treatment resources will be provided.

Smoking Usual Brand Condition. Subjects in this condition will undergo all the procedures as those subjects assigned to Camel Snus, except they will be told to smoke their usual brand of cigarettes and follow their normal patterns. At the end of the 8-week period, they will be offered the product for up to 8 weeks, with a choice of how they want to use the product. They will return to the clinic at 9, 10 and 12 weeks for assessment of use patterns (1, 2 and 4 weeks on the product). During this period, subjects will keep daily diaries via Interactive Voice Response (IVR). After 4 weeks of product use, they will come to the clinic whenever they want products for up to 8 weeks. At these clinic visits, their tobacco use patterns will be assessed via the Daily Use Summary and subjective forms. At the end of the 8 weeks (Week 16) of snus use, subjects will bring in a first morning void urine sample for analysis of tobacco exposure measures. Subjects will be paid \$50 for the Week 16 visit. Follow-up will occur as described below after the 8-week product access period (Weeks 20, 28 and 40). If subjects in the Usual Brand Condition do not choose to use the Camel Snus, they will follow the Follow-up schedule for the snus arms.

Follow-up. Follow-up clinic visit will occur for all subjects at week 20 (12 weeks after the end of the trial period). Tobacco use status (amount and type of tobacco product use) will be determined. CO will be obtained and a first morning urine and blood sample. These samples will be stored for cotinine assessment. Follow-up calls will occur at week 12 and 32 (4 and 24-weeks post-study) and tobacco use will be assessed. Those continuing to smoke or use Camel Snus will be strongly advised to quit and treatment resources will be provided.

Product Compliance Sessions. At each visit, subjects will be asked and counseled about their use of Camel Snus. The procedures for inquiry and counseling will be standardized. An intervention manual for each of the conditions will be developed.

- Complete Substitution Condition: Subjects will be asked about any concerns or obstacles associated with only using Camel Snus. If difficulties are encountered, then subjects will be asked about why they think they are experiencing difficulties (e.g., taste,

lack of satisfaction, withdrawal symptoms) and will be asked to problem solve how to deal with these difficulties so that they can meet the requirements of the protocol.

- **Partial Substitution Condition:** Subjects will be asked about their experience with using Camel Snus. Subjects in the *ad libitum* condition will be encouraged to use as much or as little as they want. Subjects in the other condition will be encouraged to follow specific instructions for use.

**Product compliance.** The importance of honest reporting will be stressed to the subjects. Compliance to the instructions for product use will be determined by: a) daily diary records; b) tobacco product logs where the amount of products dispensed will be recorded and unused products collected and recorded; and c) use of biomarkers to confirm if subjects were abstinent from combustible products (e.g., CO < 6ppm, using biomarkers for volatile constituents) in the complete substitution groups. If a subject in the complete substitution group has a CO >6, a spot urine will be collected. The sample may be used to look at toxicants related to tobacco combustion which could confirm abstinence from cigarettes.

**Compensation for Clinical Trial Phase.** Subjects will receive a nominal payment (\$5) per clinic visit to cover transportation costs for the 7 Clinical Trial Phase visits (\$40). In order to maximize abstinence in the complete substitution group, subjects will be paid for protocol compliance including staying abstinent (with biochemical confirmation) from smoking. We will use an escalating amount of money for each week of protocol compliance for all subjects (e.g., starting at \$10 and for each week of compliance, payment will increase in \$10 increment; if non-compliant with the protocol requirements, then the amount is reset to \$10). Subjects will be told that compensation is contingent on compliance and this will be monitored via their daily diaries, product accountability, completion of forms, CO levels and potentially biomarker sample levels. If CO is elevated (CO  $\geq$  6 ppm) in the complete substitution condition, a spot urine sample will be collected for analysis of biomarkers of cigarette use (e.g. thiocyanate or anabasine). Compensation for IVR completion will start at \$5 per week for week 1 of the Clinical Trial Phase and then increase \$5 per week for completion of calls, if compliant. If days are missed, the payment reverts back to the \$5 level. Subjects will receive \$40 for the follow-up visit and \$10 each for two follow-up phone calls. Total payment will be up to \$585. This procedure using contingency management has been successfully used in prior biomarker studies that required total abstinence from cigarettes (see Preliminary Studies). Subjects in the partial substitution group will undergo the same payment schedule and are paid for protocol compliance (attending visits, completing forms, submitting biosamples). The use of payment contingencies for compliance with specific instructions for use of the snus was ruled out because of the greater likelihood of false reporting and honesty of product use is critically important. Subjects will receive free Camel Snus while participating in the study.

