### **Eligibility Criteria**

Subjects must meet the following criteria for eligibility:

The inclusion criteria are the following:

- a) Male or female subjects who are at least 18 years of age;
- b) Smoking history of  $\geq 10$  cigarettes daily and  $CO > 10$  ppm or if  $CO < 10$  ppm a NicAlert equal to 6 (over  $\sim 1000$  ng/mL cotinine concentration in urine). Subjects who smoke  $> 5$  to 9 cigarettes per day will be eligible, but their NicAlert level must be equal to 6;
- c) Smoking daily for at least 1 year and no serious quit attempts in the last 3 months (to ensure stability of daily smoking, particularly for those randomized to the continued smoking group);
- d) No unstable and significant medical or psychiatric conditions as determined by medical history and Prime-MD (to ensure safety of the subject, to minimize the effects of poor health on biomarker measures and to maximize compliance to study procedures);
- e) Lack of stabilization of medications (determined by study MD);
- f) Subject has provided written informed consent to participate in the study (adolescents under the age of 18 will be excluded because this project involves continued use of tobacco products and new tobacco products);

The exclusion criteria are the following:

- a) Immune system disorders, respiratory diseases, kidney or liver diseases or any other medical disorders that may affect biomarker data;
- b) Current or recent (<3 months) alcohol or drug abuse problems;
- c) Regular tobacco use (e.g., greater than weekly or 9 days in last 30 days) other than cigarettes;

- d) Use of smokeless tobacco products within the last 3 months;
- e) Use of roll your own cigarettes that are unfiltered or not machine rolled;
- f) Currently using nicotine replacement or other tobacco cessation products (to minimize confounding effects of another product) or intention to quit in next three months;
- g) Pregnant or breastfeeding (due to toxic effects from tobacco products).
- h) Unable to read for comprehension or completion of study documents.
- i) *Clinical Trial Additional Exclusion Criteria:* Regular substance use (other than alcohol) defined as use of a substance 15 of the last 30 days. This will be assessed via the Drug Use Questionnaire-1month.

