Only week 20 at follow-up will be a clinic visit, week 12 and 32 are telephone; Samples will be stored for future funding for analysis for genetic predisposition for tobacco toxicant metabolism, behavior and harm. Abbreviations: Total NNAL: 4-(Methylnitrosamino)-1-(3-pyridyl)-1-butanol and its glucuronides; Total NNN: N'-Nitrosornornicotine and its glucuronides; PheT: r-1,t-2,3,c-4-Tetrahydroxy-1,2,3,4-tetrahydrophenanthrene; Mercapturic acids: S-Phenylmercapturic acid; Monohydroxybutylmercapturic acid; 3-Hydroxypropylmercapturic acid; 4-Hydroxybut-2-ylmercapturic acid; 2-Hydroxyethylmercapturic acid; PGE-M: 11- $\alpha$ -Hydroxy-9,15-dioxo-2,3,4,5-tetranorprostane-1,20-dioic acid; 8-epi-PGF2 $\alpha$ ; 9,11,15-Trihydroxyprosta-5,13-dien-1-oic acid. NOTE: Minor tobacco alkaloids (nornicotine, anabasine, anatabine, myosamine and cotinine) will be analyzed in 50 complete substitution subjects for the analysis proposed by Project 1.

Other biomarkers will include:

1. Exhaled carbon monoxide (CO) and oxygen saturation as indicators of the extent to which red blood cells may be carrying their usual load of oxygen.
2. Biobank: Other tobacco-related biomarkers for assessment in blood, urine, or buccal cells may be determined to be necessary or may be developed over time and these additional assays will be completed as appropriate. Also, in the future, samples may be analyzed for genetic predisposition for tobacco toxicant metabolism, behavior and harm.

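### The spot-urine check in the complete-substitution arms names a tobacco alkaloid as a cigarette marker, has two different CO triggers, and never reaches a smoker whose CO is below 6 ppm

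*Combined protocol and SAP*

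**What the plan says.** The rules for verifying abstinence in the two complete-substitution arms are spread over four places in the combined protocol and SAP.

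- **Section 6.4, Product compliance.** Compliance rests on daily diaries, product logs and biomarkers, the last described as "e.g., CO < 6ppm, using biomarkers for volatile constituents) in the complete substitution groups". Then: "If a subject in the complete substitution group has a CO >6, a spot urine will be collected". On its purpose: "The sample may be used to look at toxicants related to tobacco combustion which could confirm abstinence from cigarettes".
- **Section 6.4, Compensation for Clinical Trial Phase.** The trigger reads "If CO is elevated (CO $\geq$ 6 ppm) in the complete substitution condition", and then "a spot urine sample will be collected for analysis of biomarkers of cigarette use (e.g. thiocyanate or anabasine"). A subject judged non-compliant has the escalating weekly payment set back to its starting level.
- **Table 2, notes.** "Minor tobacco alkaloids (nornicotine, anabasine, anatabine, myosamine and cotinine) will be analyzed in 50 complete substitution subjects".
- **Section 6.2, Eligibility Criteria.** A smoker of 10 or more cigarettes a day with CO below 10 ppm may enter with "a NicAlert equal to 6". A smoker of more than 5 and up to 9 a day enters on the same NicAlert result, with no CO condition stated.

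Section 7.0 makes intent-to-treat the primary analysis. It adds compliance summaries by group and a secondary principal-stratification analysis for non-compliance, but does not say which measurements define compliance.

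**The concern.** Subjects in these arms are told to use snus and not to smoke, so a test of abstinence must respond to smoke and not to tobacco as such. A tobacco alkaloid does not meet that requirement, and the plan itself describes anabasine as one. The two section 6.4 paragraphs also give the same urine sample different purposes and different triggers.

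The second weakness lies upstream of the urine test. CO alone decides whether the sample is taken, yet entry allows smokers whose usual CO may already be under the 6 ppm line. For them a reading below 6 ppm on treatment says little about whether they stopped.

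At stake are the payment resets, which the Compensation paragraph ties to CO, diaries and possibly biomarkers. The compliance summaries and the principal-stratification analysis are also at stake, to the extent that they take their compliance variable from this check.

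**Working it through.** **1. Which subject meets which check**

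| Subject in a complete-substitution arm | CO step | Spot urine | Possible error |
|---|---|---|---|
| Abstinent, CO below 6 | pass | not taken | none |
| Abstinent, CO above 6 | flagged | taken | wrongly failed if presence of anabasine counts as smoking, because snus is a source too |
| Smoking, CO below 6 | pass | not taken | missed by CO and urine; left to diary and volatile biomarkers |
| Smoking, CO above 6 | flagged | taken | a combustion marker can confirm; anabasine cannot tell the source |
| Anyone at exactly 6 ppm | not below 6, so fails the Product compliance criterion | not taken under Product compliance, taken under Compensation | rule undefined |

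In the last row, the abstinence criterion of CO below 6 in the Product compliance paragraph agrees with the trigger of 6 or more in the Compensation paragraph. It does not agree with the trigger in its own paragraph.

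**2. What else could catch a low-CO smoker**

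- Product logs record snus dispensed and returned. Section 6.4 says cigarettes are not supplied, so the logs cannot show smoking.
- Diaries are self-report. The Compensation paragraph declines to pay for following the snus instructions because that would invite false reports; the same incentive applies to abstinence, which is paid.
- Volatile-constituent biomarkers are named without being conditional on CO, but only as an example in one paragraph and as a possibility in the other. No marker, visit or cut-off is fixed.

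**3. What a size would depend on**

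From the plan (section 7.0, Sample-size determination): 138 per group × 5 = 690; the two complete-substitution arms hold 2 × 138 = 276 before dropout; planned abstinence a = 40 to 50%. The derivation of 138 cannot be reproduced, because alpha, sidedness, a numeric effect size and the dropout rate are not stated there. Nothing here depends on it.

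Not in the documents, so assumed: p, the share of continuing smokers with CO below 6 ppm; and f, the share of abstainers with CO at or above 6 ppm.

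Smokers missed by CO = 276 × (1 − a) × p. If no other check catches them, apparent abstinence = a + (1 − a) × p.

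| p (assumed) | a = 40% (165.6 smokers) | a = 50% (138 smokers) |
|---|---|---|
| 2% | 3.3 missed; reads 41.2% | 2.8 missed; reads 51.0% |
| 5% | 8.3; 43.0% | 6.9; 52.5% |
| 10% | 16.6; 46.0% | 13.8; 55.0% |
| 20% | 33.1; 52.0% | 27.6; 60.0% |

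Abstainers wrongly failed, if anabasine were the marker and any amount counted as smoking = 276 × a × f. Apparent abstinence = a × (1 − f).

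| f (assumed) | a = 40% (110.4 abstainers) | a = 50% (138 abstainers) |
|---|---|---|
| 5% | 5.5 failed; reads 38.0% | 6.9 failed; reads 47.5% |
| 10% | 11.0; 36.0% | 13.8; 45.0% |
| 20% | 22.1; 32.0% | 27.6; 40.0% |

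With both errors, apparent abstinence = a(1 − f) + (1 − a)p. At a = 50% and p = f = 20% this is 0.40 + 0.10 = 50%, the true rate. A plausible overall rate therefore does not show that individuals were classified correctly. These tables show sensitivity to p and f; they are not estimates.

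**The case against.** The best defence is that the plan commits to very little here. Anabasine is one of two examples. The Product compliance paragraph points to combustion toxicants instead and says only that the sample may be used. No cut-off appears, and no rule makes any amount of anabasine a failure. A false failure needs three things together: an abstainer with raised CO, anabasine chosen as the assay, and its presence taken as proof of smoking. This stands. The text permits the error; it does not make it happen.

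A reader might infer that low-CO smokers cannot fail, or that they pass every check. The documents do not support that. The entry exception covers CO below 10 ppm, and admitted smokers above 6 ppm and below 10 ppm do trip the trigger. Table 2 schedules CO at weeks 1, 2, 3, 4, 6 and 8, so a smoker must read low each time to go unflagged throughout. Diaries and volatile biomarkers also remain.

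A reader might also put a number on the contamination. If 5 to 15% have usual CO below 6 and 50 to 60% of them smoke, the missed smokers are 276 × 0.05 × 0.5 = 6.9 to 276 × 0.15 × 0.6 = 24.8. That is 6.9/(138 + 6.9) = 4.8% to 24.8/(110.4 + 24.8), about 18%, of the group labelled abstinent. The arithmetic is right, but the 5 to 15% has no source in the documents, and the sum assumes that no other check catches anyone and that nobody drops out.

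Finally, section 7.0 does not tie its compliance variable to the spot urine, so an effect on that analysis is conditional. What the defence leaves untouched is that a marker unable to distinguish the two products is labelled a marker of cigarettes, that the two paragraphs disagree, and that no firm rule covers the smoker below 6 ppm.

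**Conclusion.** The point holds as a defect in how abstinence is verified. Three things follow from the documents alone: anabasine cannot show smoking in subjects assigned a tobacco product; the purpose and trigger of the spot urine are stated inconsistently; and a continuing smoker below 6 ppm is outside the reach of CO and of the urine it triggers.

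How many subjects would be misclassified cannot be derived, because neither p nor f is given and no decision rule is stated. It would go too far to say that misclassification in both directions has been demonstrated.

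The primary intent-to-treat comparison does not use this classification and is not directly affected. Payment resets are exposed. The compliance summaries and the principal-stratification analysis are exposed only as far as they adopt this check. The correction is worth making because it is cheap and because one of the named markers is wrong for its purpose, not merely underspecified.

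**What to change.** 1. In the Compensation paragraph, delete anabasine and name a combustion marker consistent with the Product compliance paragraph, with its cut-off and a statement of whether the triggered sample is always assayed.
2. Use one CO trigger in both paragraphs. Six ppm or more matches the abstinence criterion of below 6 already stated.
3. In section 7.0, define the compliance variable. For the complete-substitution arms, base it on the mercapturic acids at weeks 4 and 8 regardless of CO, with a cut-off fixed before analysis. The documents give none.
4. Do not accept CO alone as confirmation when baseline CO was already below the cut-off. Table 2 has CO at both baseline visits, so these subjects can be identified, and their share gives a first indication of p.

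**Cost.** This is protocol and SAP wording. Table 2 schedules the mercapturic acids at weeks 4 and 8, and the clinic-visit procedures say samples from those weeks will be analysed, so no new collection is needed. The Measures section speaks of assaying some or all of the panel, so these assays would have to become a firm commitment in these arms.

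**Downsides to state.** Results arrive after the visit, so payment decisions would still rest on CO. Mercapturic acids are also Hypothesis 1 outcomes: comparing them among compliers defined by them would be circular. Compliance defined this way should serve analyses of NNAL and other outcomes, not complier comparisons of the mercapturic acids.
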